6.3 Patient Data Profiles

A Patient Data Profile listing will be provided. It will contain demographic information, randomization information, all endpoint assessments and laboratory measurements. See_Appendix B, Data Listing 17 for full details. Some variation in the appearance of this table is acceptable to accommodate unformatted SAS® output provided that all information is present.

7.0 List of Analysis Tables, Figures and Listings

Table No.	Table Title	Included in Final Tables	Shown in Appendix B
1	Subject Disposition	Х	Х
2	Demographics and Baseline Data Summary Statistics – Continuous Variables (Safety Population)	х	х
3	Demographics and Baseline Data Summary Statistics – Categorical Variables (Safety Population)	x	х
4	Summary of Study Drug Administration and Compliance (Safety Population)	х	х
5	QMG Total Score Summary Statistics by Time Point (FAS Population)	х	х
6	QMG Total Score Summary Statistics by Time Point (PP Population)	x	
7	QMG Total Score Summary Statistics by Time Point and Dose Group (FAS Population)	x	х
8	QMG Total Score Summary Statistics by Time Point and Dose Group (PP Population)	x	
9	QMG Item Scores Summary Statistics by Time Point (FAS Population)	х	х
10	QMG Item Scores Summary Statistics by Time Point (PP Population)	Х	
11	QMG Item Scores Summary Statistics by Time Point and Dose Group (FAS Population)	х	х
12	QMG Item Scores Summary Statistics by Time Point and Dose Group (PP Population)	х	
13	QMG Total Score CFB Analysis (FAS Population)	Х	Х
14	QMG Total Score CFB Analysis (PP Population)	Х	
15	QMG Item Scores CFB Analysis (FAS Population)	Х	Х
16	QMG Item Scores CFB Analysis (PP Population)	Х	
17	SGI Score Summary Statistics by Time Point (FAS Population)	х	х
18	SGI Score Summary Statistics by Time Point (PP Population)	Х	
19	SGI Score Summary Statistics by Time Point and Dose Group (FAS Population)	х	х
20	SGI Score Summary Statistics by Time Point and Dose Group (PP Population)	x	
21	SGI Score CFB (FAS Population)	Х	Х
22	SGI Score CFB Analysis (PP Population)	X	
23	QMG Total Score and SGI Score Sensitivity Analysis (FAS Population)	x	х
24	QMG Total Score and SGI Score Sensitivity Analysis (PP Population)	х	
25	CGI-I Scores Summary Statistics (FAS Population)	Х	Х
26	CGI-I Scores Summary Statistics (PP Population)	Х	
27	CGI-I Scores Summary Statistics by Dose Group (FAS Population)	Х	х
28	CGI-I Scores Summary Statistics by Dose Group (PP Population)	Х	

Table No.	Table Title	Included in Final Tables	Shown in Appendix B
29	Number and Proportion of Subjects with ≥ 20% Increase in 3TUG Average Time (FAS Population)	Х	х
30	Number and Proportion of Subjects with ≥ 20% Increase in 3TUG Average Time (PP Population)	Х	
31	Number and Proportion of Subjects with ≥ 20% Increase in 3TUG Average Time by Dose Group (FAS Population)	х	х
32	Number and Proportion of Subjects with ≥ 20% Increase in 3TUG Average Time by Dose Group (PP Population)	Х	
33	Summary of Patient Most Bothersome Symptom (FAS Population)	х	х
34	Summary of Patient Most Bothersome Symptom (PP Population)	Х	
35	Summary of Patient Most Bothersome Symptom by Dose Group (FAS Population)	х	x
36	Summary of Patient Most Bothersome Symptom by Dose Group (PP Population)	Х	
37	QMG Total Score Summary Statistics by Limb Domain and Time Point (FAS Population)	х	x
38	QMG Total Score Summary Statistics by Limb Domain and Time Point (PP Population)	х	
39	Limb Domain Specific QMG Total Score CFB Analysis (FAS Population)	х	х
40	Limb Domain Specific QMG Total Score CFB Analysis (PP Population)	х	
41	Number and Percent of Subjects with Treatment Emergent Adverse Events (Safety Population)	Х	х
42	Number and Percent of Subjects with Treatment Emergent Adverse Events by Dose Level (Safety Population)	х	x
43	Summary of Treatment Emergent Adverse Events (Safety Population)	х	x
44	Number and Percent of Subjects with Serious Treatment Emergent Adverse Events (Safety Population)	Х	x
45	Number and Percent of Subjects with Treatment Emergent Adverse Events by Relationship to Treatment (Safety Population)	х	x
46	Number and Percent of Subjects with Treatment Emergent Adverse Events by Severity Grade (Safety Population)	х	х
47	Vital Sign Parameters Summary Statistics (Safety Population)	Х	x
48	Number and Percent of Subjects Taking Concomitant Medications by ATC Level 3 and Preferred Term (Safety Population)	х	x

Listing No.	Data Listing Title	Included in Final Listings	Shown in Appendix B
DL1	Subject Disposition Data Listing	X	Х
DL2	Protocol Deviations Data Listing	Х	Х
DL3	Demographics Data Listing	X	Х
DL4	Subjects Excluded from FAS Population Data Listing	X	X
DL5	Subjects Excluded from PP Population Data Listing	Х	Х
DL6	Medical History Data Listing	Х	Х
DL7	Prior and Concomitant Medications Data Listing	Х	Х
DL8	Adverse Events Data Listing	Х	Х
DL9	Physical Exam Data Listing	Х	Х
DL10	Vital Signs Data Listing	Х	Х
DL11	Study Drug Administration Data Listing	Х	Х
DL12	SGI Data Listing	Х	Х
DL13	QMG Data Listing	Х	Х
DL14	CGI-I Data Listing	Х	Х
DL15	3TUG Data Listing	Х	Х
DL16	Patient Most Bothersome Symptom Data Listing	Х	Х
DL17	Patient Data Profile	Х	Х

Appendix A – Tables, Figures and Listing Specifications

Orientation

Tables, figures, and listings will be displayed in landscape.

Margins

Margins will be 1 inch on all sides. Table, figure, and listing boundaries will not extend into the margins.

Font

Courier New, 8 point.

Headers

The table number will be on the second line of the title area. The title area will contain the Sponsor name, the study number, and the name of the table. The title area will contain the page number (Page x of y) on the far right, one line above the name of the table.

Footers

- The first line will be a solid line.

- Next will be any footnotes regarding information displayed in the table.
- The last line will display the name of the SAS program that generated the table and (if applicable) the source data reference.

Table Disclaimer

The format of the mock tables shown in the appendix of this Statistical Analysis Plan (SAP) will be the format of the deliverable tables to the extent that Word document constructed tables can match production tables produced by SAS. This formatting includes the content and format of the header and footer areas of the tables. The Sponsor agrees to the format of the tables as shown in the appendix.

Further programming charges will be applicable for changes in the format of tables (including title statements, notes, data dependent footnotes, etc.) made after the approval of the SAP.

Missing Values

All missing values will be displayed on the output tables/listings as blanks.

Computation Values for Study Dates

The date format to be used is dd-mmm-yyyy. Missing parts of dates are not shown (e.g., for a missing day value, the value displayed is in mmm-yyyy format). When date computations are necessary, the following table indicates the substitutions used in order to make those computations.

Scenario	Value Used for Computations
Start date – Missing month and day values	January 1 of the indicated year
Start date – Missing day values	The first day of the indicated month
Stop date – Missing month and day values	December 31 of the indicated year
Stop date – Missing day values	The last day of the indicated month

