REB research ethics board
SAE(s) serious adverse event(s)
SBP systolic blood pressure
SGI subject global impression
SOPs standard operating procedures
SFEMG single fiber electromyogram

t_{1/2} elimination half-life

TEAE(s) treatment emergent adverse event(s)

TID three times daily
TK toxicokinetic

T_{max} time to reach maximum plasma concentration

TPE Therapeutic Plasma Exchange

US United States

Definition of Terms:

Investigational Product (IP):

"A pharmaceutical form of an active ingredient or placebo being tested or used as a reference in a clinical trial, including a product with a marketing authorization when used or assembled (formulated or packaged) in a way different from the approved form, or when used for an unapproved indication, or when used to gain further information about an approved use" (from International Conference on Harmonisation of Technical Requirements for Registration of Pharmaceuticals for Human Use ICH Harmonised Tripartite Guideline: Guideline for Good Clinical Practice E6 [ICH E6]). The terms "IP" and "study drug" may be used interchangeably in the protocol.

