8.1 Overall Study Design and Plan

This randomized (1:1), double-blind, placebo-controlled, parallel-group study is designed to evaluate the efficacy and safety of amifampridine phosphate in patients diagnosed with LEMS. Patients will have been receiving unblinded drug treatment in the expanded access program (EAP-001), after which blinded treatment effect will be assessed for continuation or cessation of drug. The study is planned to include approximately 28 male and female patients. The planned duration of participation for each patient is 5 days, excluding the screening period, which can last up to 7 days.

Those patients successfully satisfying all screening criteria will be randomized to a treatment group. Amifampridine phosphate (at the patient's optimal dose) or placebo will be dispensed by the site pharmacist, according to the randomization schedule, to begin with the next dose after all Day 0 assessments are completed and continued for 4 days. After completion of the study, patients will be eligible for expanded access treatment program with open-label amifampridine phosphate. Since patients will have been out of the expanded accesss program for less than 30 days, as LMS-003 participants, rescreening to return to expanded access program will not be required, per the protocol, and patients may immediately resume their participation in the expanded access program (EAP-001).

Page 29

Screening

Patients receiving amifampridine phosphate treatment for LEMS, and meeting the inclusion and exclusion criteria are eligible to participate in this study. They can be randomized if on stable dose and frequency of amifampridine phosphate for at least 1 week before being randomized to a treatment. Screening and randomization (Day 0) may be combined into a single visit.

Treatment (Days 1-4) (+1 day)

Patients will be randomized (1:1 ratio) on the last day of the screening period (Day 0) to either amifampridine phosphate or placebo. Beginning with the next dose after all Day 0 assessments are completed, the patient will take, under double-blind conditions, either amifampridine phosphate tablets or placebo tablets through Day 4, with a clinic visit on the last day (Day 4) for assessments (Table 3). Any unused portion of dispensed drug will be returned to the pharmacy.

During the study, safety and efficacy assessments will be made as detailed in the Schedule of Assessments in Table 3.

Table 3. Schedule of Assessments

	Samaaning	Randomization	Days 1-4

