13.3 Safety Analysis

Safety analyses will be conducted on the Safety Population. The safety analysis will be descriptive and will be presented using observed data only.

All AEs will be coded using the Medical Dictionary for Regulatory Activities (MedDRA). Only TEAEs will be included in the safety analysis. The incidence of TEAEs will be summarized by system organ class, preferred term, relationship to IP, and severity by treatment. Deaths, SAEs, and AEs leading to premature discontinuation will be listed. Vital signs, ECGs, physical examination data, and concomitant medications will also be summarized. Routine laboratory assessments will not be performed. Laboratory evaluations, if performed, will be listed.

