1.2 Study Procedures

The planned duration of participation for each subject is 5 days (Day 0 through Day 4), excluding the screening period, which can last up to 7 days. Those subjects satisfying all inclusion and exclusion criteria will be randomized to a Treatment Group on the last day of the screening period (Day 0). The treatment period will take place on the remainder of Day 0 and Days 1 through 4. The following assessments will be performed at the beginning and end of the 4-day treatment period:

- Vital signs
- Urine sample for amifampridine level (collected at days 3, and 4)
- Clinical Global Impression of Improvement (CGI-I)
- Subject Global Impression (SGI)
- Quantitative Myasthenia Gravis (QMG)
- Triple Timed Up and Go (3TUG)
- Patient most bothersome symptom question
- Record concomitant medications
- Monitor for adverse events (throughout the 5-day treatment period)

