5.0 Analysis of Safety

The safety variables for this study are:

- Adverse events (AE)
- Vital signs (screening, Days 1-4)

- Physical examination (at screening only)
- Concomitant medications

Adverse Events

All AEs will be observed for each subject from enrollment until termination from the study. Prior to analysis, all AEs will be coded using MedDRA. Based on these coded terms, treatment emergent AEs (TEAEs) will be summarized using system organ class and preferred term by treatment and overall for all subjects in the safety population. This analysis will be repeated for serious TEAEs (TESAEs).

TEAEs will also be summarized by severity and relationship to IP. An overall summary table will provide the highest relationship and maximum severity observed per subject, as well as the counts of subjects with at least one TESAE.

All AEs will be listed, regardless of whether or not they were treatment emergent. AEs having an end date prior to signing the informed consent for this study will not be displayed in the AE data listings.

Vital Signs

Summary statistics (mean, median, sample size, standard deviation, minimum, and maximum) will be computed on the raw and change from baseline values for each vital sign parameter by time point, for each treatment. The screening time point will serve as baseline. If there are multiple vital signs taken at any time point, then the latest set of vital signs will be used for the analysis. All vital sign data will be listed.

Physical Exam

The physical exam data collected at screening will be listed.

Concomitant Medications

A table of the WHO-coded medications will be constructed by treatment group and overall with medications summarized by level 3 anatomical therapeutic chemical (ATC) term and Preferred Term. The number and percent of subjects on each drug will be summarized. A data listing for all concomitant medications will be provided.

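### The SAP's first-of-month rule for partial start dates has no adverse-event exception and, under the usual TEAE definition, would date about 90% of day-missing on-treatment events before the first blinded dose

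*SAP*

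**What the plan says.** SAP Appendix A, under the heading on computation values for study dates, gives one general rule: "When date computations are necessary, the following table indicates the substitutions used in order to make those computations". A start date with a missing day becomes "The first day of the indicated month"; one with month and day missing becomes "January 1 of the indicated year". The table does not separate adverse events from medications or medical history, and it makes no exception for the month of first dose.

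On the dosing window, SAP Section 1.2 states: "The treatment period will take place on the remainder of Day 0 and Days 1 through 4". Protocol Section 8.1 lets the Day 4 visit slip by one day.

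On what is analysed, Protocol Section 13.3 states: "Only TEAEs will be included in the safety analysis". SAP Section 5.0 says that "treatment emergent AEs (TEAEs) will be summarized using system organ class and preferred term by treatment and overall for all subjects in the safety population", and repeats this for serious TEAEs, severity and relationship (Tables 41 to 46). The same section lists every adverse event, emergent or not, in Data Listing 8.

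TEAE is expanded in the Protocol's abbreviation list but defined in neither document. SAP Section 2.3 says that missing values will not be imputed and that analyses rest on observed data. It does not mention the substitutions in Appendix A.

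**The concern.** An adverse event is normally sorted as treatment-emergent by comparing its onset with the first dose. Setting an unknown day to the 1st is a familiar default, and over months of treatment it does little harm. Here treatment lasts five calendar days, so the 1st of the month will usually fall before the first blinded dose even when the event began on blinded drug. A programmer who applies Appendix A literally would flag that event as not emergent and leave it out of the TEAE summaries, including Table 44 for serious TEAEs.

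Confirming safety and tolerability through adverse event reports is a primary objective in Protocol Section 7.1. For safety, an uncertain onset would ordinarily be resolved by counting the event; this rule resolves it by removing the event.

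**Working it through.** The plan gives no figure on this point, so there is none to reproduce.

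**Inputs from the documents**
- Substitution rule: SAP Appendix A.
- Window: Day 0 to Day 4, five calendar days (SAP Section 1.2); six with the extra day (Protocol Section 8.1).
- Sample: about 28 patients randomized 1:1 (Protocol Section 8.1), so about 14 per arm.

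**Assumptions**
- TEAE means onset on or after the date of first blinded dose, taken as Day 0.
- First-dose dates are spread evenly over the calendar, and true onset evenly over the days of the window.

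**Step 1: direction.** The 1st of the onset month is never later than the true onset. The substitution can therefore move an on-treatment event to before first dose, but can never move a pre-dose event into the treatment period.

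**Step 2: one 30-day month.** There are 30 × 5 = 150 combinations of Day 0 date and onset day. The substituted date is on or after Day 0 only if:
- Day 0 is the 1st: 5 combinations; or
- onset falls in the next month, with Day 0 on the 27th, 28th, 29th or 30th: 1 + 2 + 3 + 4 = 10 combinations.

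Misplaced: (150 − 5 − 10)/150 = 135/150 = 90%.

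**Step 3: a full 365-day year.** There are 365 × 5 = 1,825 combinations.
- Substituted date equal to Day 0: 12 × 5 = 60, or 3.3%.
- Substituted date after Day 0: 12 × 10 = 120, or 6.6%.
- Substituted date before Day 0: 1,825 − 60 − 120 = 1,645, or 90.1%.

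**Step 4: range for a missing day**

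| Onset assumed | Dated before first dose |
|---|---|
| Day 0 only | (365 − 12)/365 = 96.7% |
| Day 4 only | (365 − 12 − 48)/365 = 83.6% |
| Days 0 to 5 (extra day used) | (2,190 − 72 − 180)/2,190 = 88.5% |

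**Step 5: month and day both missing.** Only a Day 0 on 1 January (5 combinations) or a window that crosses the year end (10) escapes: (1,825 − 15)/1,825 = 99.2%.

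**Step 6: weight of one patient.** 1/14 = 7.1 percentage points of incidence in a summary row, if the lost event was that patient's only event in the row.

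**Step 7: effect of the opposite rule.** If a partial date in the first-dose month is set to the first-dose date, no on-treatment event is lost. If that is done with no further condition, day-missing events that began 1 to 7 days before first dose become emergent unless they fall in the previous month: (365 × 7 − 12 × 28)/(365 × 7) = 2,219/2,555 = 86.8%. The Appendix A rule counts none of these.

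**The case against.** The strongest objection is that the key step is not written down. TEAE is undefined, nothing says that the substituted date sets the flag, the rule sits in a formatting appendix, and Section 2.3 disclaims imputation. This stands: the effect is conditional. It does not remove the point, because Appendix A applies whenever a date computation is needed, the Data Listing 8 shell prints adverse event start beside treatment start, and the documents offer no other criterion.

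A reader might infer that the event vanishes from all safety output. The documents do not support that. Only Tables 41 to 46 are exposed; Tables 47 and 48 do not use adverse event dates. The event stays in Data Listing 8 and in the patient profile (Data Listing 17), and Appendix A displays the date as partial. Serious events are further protected: Protocol Section 13.3 calls for SAEs to be listed, and Section 9.2 requires reporting within 24 hours.

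Partial dates may also be rare. Events are assessed on Day 0 and Day 4, so recall is short, and the listing carries onset date and time. The likelier source is unresolved events copied from the expanded access log (Protocol Section 9.1), for which a pre-dose date is correct. This stands too, and it limits the practical effect.

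Finally, the rule is the same in both arms, so no between-arm bias is shown, and an unguarded opposite rule would over-count heavily (Step 7). Both are fair. The second is a reason to attach conditions to the replacement.

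**Conclusion.** The point holds in conditional form. If TEAE means onset on or after the first blinded dose and Appendix A is applied as written, about 90% of true on-treatment events with a missing start day would be dated before first dose (83.6% to 96.7% by onset day), and about 99% with the month also missing. Those events would leave Tables 41 to 46 but remain in the listings and the patient profile.

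The percentages assume evenly spread dates and apply only to partially dated events. The documents do not say how many there will be; probably few. The expected effect on the results is therefore small. It still merits correction because the error runs only toward fewer events, arms of about 14 make single patients visible, and the underlying gap, an undefined TEAE, should be closed in any case. It would be wrong to conclude that on-treatment events will almost always be lost or that serious events will go unreported.

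**What to change.** Before database lock:

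1. In SAP Section 5.0, define TEAE as an adverse event with onset or worsening on or after the first dose of blinded study drug.
2. In Appendix A, add a rule for adverse event start dates only. Use the date of first blinded dose when all of these hold:
   - the known part of the start date matches the month and year (or the year) of that dose;
   - the stop date is not before that dose;
   - the event was not carried over from expanded access;
   - the event was not already recorded at the screening or Day 0 pre-dose adverse event assessment.
3. Keep the current rule for medications and medical history.
4. In Section 2.3, state that the Appendix A date substitutions are the exception to the no-imputation statement.

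The cost is a few SAP sentences and a short piece of code. The downside is that some partially dated events that began shortly before first dose will be counted as treatment-emergent. Without conditions that share would be about 87% of day-missing events from the preceding week; the conditions remove those that stopped before first dose, were carried over, or were already on record. What remains errs toward counting events, the conservative direction for safety.

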Appendix B – Table Shells

		Amifampridine	Placebo	Overall
Screen Failures				XX
Enrolled		XX	xx	XX
	Low Dose (< 60 mg/day)	xx (xxx%)	xx (xxx%)	xx (xxx%)
	High Dose (\geq 60 mg/day)	xx (xxx%)	xx (xxx%)	xx (xxx%)
Completed		xx (xxx%)	xx (xxx%)	xx (xxx%)
	Low Dose (< 60 mg/day)	xx (xxx%)	xx (xxx%)	xx (xxx%)
	High Dose (\geq 60 mg/day)	xx (xxx%)	xx (xxx%)	xx (xxx%)
Withdrawn		xx (xxx%)	xx (xxx%)	xx (xxx%)
	Low Dose (< 60 mg/day)	xx (xxx%)	xx (xxx%)	xx (xxx%)
	High Dose (\geq 60 mg/day)	xx (xxx%)	xx (xxx%)	xx (xxx%)
Reason for Withdrawal	Adverse Event	xx (xxx%)	xx (xxx%)	xx (xxx%)
	Low Dose (< 60 mg/day)	xx (xxx%)	xx (xxx%)	xx (xxx%)
	High Dose (> 60 mg/day)	xx (xxx%)	xx (xxx%)	xx (xxx%)
	Lost To Follow-Up	xx (xxx%)	xx (xxx%)	xx (xxx%)
	Low Dose (< 60 mg/day)	xx (xxx%)	xx (xxx%)	xx (xxx%)
	High Dose (> 60 mg/day)	xx (xxx%)	xx (xxx%)	xx (xxx%)
	Death	xx (xxx%)	xx (xxx%)	xx (xxx%)
	Low Dose (< 60 mg/day)	xx (xxx%)	xx (xxx%)	xx (xxx%)
	High Dose (> 60 mg/day)	xx (xxx%)	xx (xxx%)	xx (xxx%)
	Physician Decision	xx (xxx%)	xx (xxx%)	xx (xxx%)
	Low Dose (< 60 mg/day)	xx (xxx%)	xx (xxx%)	xx (xxx%)
	High Dose (> 60 mg/day)	xx (xxx%)	xx (xxx%)	xx (xxx%)
	Protocol Deviation	xx (xxx%)	xx (xxx%)	xx (xxx%)
	Low Dose (< 60 mg/day)	xx (xxx%)	xx (xxx%)	xx (xxx%)
	High Dose (\geq 60 mg/day)	xx (xxx%)	xx (xxx%)	xx (xxx%)
	Study Terminated by Sponsor	xx (xxx%)	xx (xxx%)	xx (xxx%)
	Low Dose (< 60 mg/day)	xx (xxx%)	xx (xxx%)	xx (xxx%)
	High Dose (> 60 mg/day)	xx (xxx%)	xx (xxx%)	xx (xxx%)
	Withdrawal by Subject	xx (xxx%)	xx (xxx%)	xx (xxx%)
	Low Dose (< 60 mg/day)	xx (xxx%)	xx (xxx%)	xx (xxx%)
	High Dose (\geq 60 mg/day)	xx (xxx%)	xx (xxx%)	xx (xxx%)
	Other	xx (xxx%)	xx (xxx%)	xx (xxx%)
	Low Dose (< 60 mg/day)	xx (xxx%)	xx (xxx%)	xx (xxx%)
	High Dose (\geq 60 mg/day)	xx (xxx%)	xx (xxx%)	xx (xxx%)

Table 1. Subject Disposition Catalyst Pharmaceuticals, Inc. - LMS-003

The denominator for all percentages in the table is the number of enrolled subjects in the pertinent treatment/dose group and overall. Table Creation Date: (DD-MMM-YYYY) Source Program: xxxxxx.sas Source Listing: Data Listing 1

Page x of y

Table 2. Demographics and Baseline Data Summary Statistics - Continuous Variables Catalyst Pharmaceuticals, Inc. - LMS-003 Safety Population (N=xxx)

Variable	Treatment Group	Mean	Std Dev	n	Min	Max	Median
Age (years)	Amifampridine	XXX	XXX	XXX	XXX	XXX	XXX
	Low Dose (< 60 mg/day)	XXX	XXX	XXX	XXX	XXX	XXX
	High Dose (> 60 mg/day)	XXX	XXX	XXX	XXX	XXX	XXX
	Placebo	XXX	XXX	XXX	XXX	XXX	XXX
	Low Dose (< 60 mg/day)	XXX	XXX	XXX	XXX	XXX	XXX
	High Dose (> 60 mg/day)	XXX	XXX	XXX	XXX	XXX	XXX
	Overall	XXX	XXX	XXX	XXX	XXX	XXX
Baseline Weight (kg)	Amifampridine	XXX	XXX	XXX	XXX	XXX	XXX
	Low Dose (< 60 mg/day)	XXX	XXX	XXX	XXX	XXX	XXX
	High Dose (> 60 mg/day)	XXX	XXX	XXX	XXX	XXX	XXX
	Placebo	XXX	XXX	XXX	XXX	XXX	XXX
	Low Dose (< 60 mg/day)	XXX	XXX	XXX	XXX	XXX	XXX
	High Dose (> 60 mg/day)	XXX	XXX	XXX	XXX	XXX	XXX
	Overall	XXX	XXX	XXX	XXX	XXX	XXX

Table Creation Date: (DD-MMM-YYYY) Source Program: xxxxxx.sas Source Listing: Data Listing 3

Table 3. Demographics and Baseline Data Summary Statistics - Categorical Variables Catalyst Pharmaceuticals, Inc. - LMS-003 Safety Population (N=xxx)

Demographics Variable	Category	Amifampridine (N=xxx)	Placebo (N=xxx)	Overall (N=xxx)
Gender	Male	xxx (xxx%)	xxx (xxx%)	xxx (xxx%)
	Low Dose (< 60 mg/day)	XX (XXX ^{%a})	xx (xxx%)	xx (xxx%)
	High Dose (> 60 mg/day)	XX (XXX%)	xx (xxx%)	xx (xxx%)
	Female	xxx (xxx%)	xxx (xxx%)	xxx (xxx%)
	Low Dose (< 60 mg/day)	xx (xxx%)	xx (xxx%)	xx (xxx%)
	High Dose (> 60 mg/day)	xx (xxx%)	xx (xxx%)	XX (XXX%)
Ethnicity	Hispanic or Latino	xxx (xxx%)	xxx (xxx%)	xxx (xxx%)
	Low Dose (< 60 mg/day)	xx (xxx%)	xx (xxx%)	xx (xxx%)
	High Dose (> 60 mg/day)	xx (xxx%)	xx (xxx%)	xx (xxx%)
	Not Hispanic or Latino	xxx (xxx%)	xxx (xxx%)	xxx (xxx%)
	Low Dose (< 60 mg/day)	xx (xxx%)	xx (xxx%)	xx (xxx%)
	High Dose (> 60 mg/day)	xx (xxx%)	xx (xxx%)	xx (xxx%)

^a Denominator for treatment/class/dose percentages is the treatment/class/dose level total. Table Creation Date: (DD-MMM-YYYY) Source Program: xxxxxx.sas Source Listing: Data Listing 3

Page	v	of	37
rage	x	OL	y

Table 4. Summary of Study Drug Administration and Compliance Catalyst Pharmaceuticals, Inc. - LMS-003 Safety Population (N=xxx)

	Statistic	Amifampridine (N=xxx)	Placebo (N=xxx)
Duration (days)	n Mean (SD)	xxx xxx (xxx)	xxx xxx (xxx)
	Median	XXX (XXX) XXX	XXX (XXX) XXX
	Minimum, Maximum	XXX, XXX	XXX, XXX
Compliance (%)	n	XXX	XXX
	Mean (SD)	XXX (XXX)	XXX (XXX)
	Median	XXX	XXX
	Minimum, Maximum	XXX, XXX	XXX, XXX

Table Creation Date: (DD-MMM-YYYY) Source Program: xxxxxx.sas Source Listing: Data Listing 11

Table 5. QMG Total Score Summary Statistics by Time Point Catalyst Pharmaceuticals, Inc. - LMS-003 FAS Population (N=xxx)

Treatment	Time Point ^a	Data Type ^b	Mean	Std Dev	n	Min	Max	Median
Amifampridine	Dav 0 (Baseline)	RAW						
Amillampilalie	_ · · ,		XXX	XXX	XXX	XXX	XXX	XXX
	Post-Baseline	RAW	XXX	XXX	XXX	XXX	XXX	XXX
		CFB	XXX	XXX	XXX	XXX	XXX	XXX
Placebo	Day 0 (Baseline)	RAW	XXX	XXX	XXX	XXX	XXX	XXX
	Post-Baseline	RAW	XXX	XXX	XXX	XXX	XXX	XXX
		CFB	XXX	XXX	XXX	XXX	XXX	XXX

^a The post-treatment result will be the result obtained on Day 4, unless the subject discontinued treatment early, in which case the post-treatment result may be obtained at an earlier time point. ^b RAW = observed data entered in the database; CFB = change from baseline. Table Creation Date: (DD-MMM-YYYY) Source Program: xxxxxxx.sas

Source Listing: Data Listing 14

Table 7. QMG Total Score Summary Statistics by Time Point and Dose Group Catalyst Pharmaceuticals, Inc. - LMS-003 FAS Population (N=xxx)

			Data		Std				
Treatment	Dose Group	Time Point ^a	Typeb	Mean	Dev	n	Min	Max	Median
Amifampridine									
	Low Dose (< 60mg/day)	Day 0 (Baseline)	RAW	XXX	XXX	XXX	XXX	XXX	XXX
		Post-Baseline	RAW	XXX	XXX	XXX	XXX	XXX	XXX
			CFB	XXX	XXX	XXX	XXX	XXX	XXX
	High Dose (> 60mg/day)	Day O (Baseline)	RAW	XXX	XXX	XXX	XXX	XXX	XXX
		Post-Baseline	RAW	XXX	XXX	XXX	XXX	XXX	XXX
			CFB	XXX	XXX	XXX	XXX	XXX	XXX
	All Doses	Day O (Baseline)	RAW	XXX	XXX	XXX	XXX	XXX	XXX
		Post-Baseline	RAW	XXX	XXX	XXX	XXX	XXX	XXX
			CFB	XXX	XXX	XXX	XXX	XXX	XXX
Placebo									
	Low Dose (< 60mg/day)	Day O (Baseline)	RAW	XXX	XXX	XXX	XXX	XXX	XXX
		Post-Baseline	RAW	XXX	XXX	XXX	XXX	XXX	XXX
			CFB	XXX	XXX	XXX	XXX	XXX	XXX
	High Dose (> 60mg/day)	Day O (Baseline)	RAW	XXX	XXX	XXX	XXX	XXX	XXX
		Post-Baseline	RAW	XXX	XXX	XXX	XXX	XXX	XXX
			CFB	XXX	XXX	XXX	XXX	XXX	XXX
	All Doses	Day O (Baseline)	RAW	XXX	XXX	XXX	XXX	XXX	XXX
		Post-Baseline	RAW	XXX	XXX	XXX	XXX	XXX	XXX
			CFB	XXX	XXX	XXX	XXX	XXX	XXX

^a The post-treatment result will be the result obtained on Day 4, unless the subject discontinued treatment early, in which case the post-treatment result may be obtained at an earlier time point.

^b RAW = observed data entered in the database; CFB = change from baseline.

Table Creation Date: (DD-MMM-YYYY)

Source Program: xxxxxx.sas

Source Listing: Data Listing 14

Table 9. QMG Item Scores Summary Statistics by Time Point Catalyst Pharmaceuticals, Inc. - LMS-003 FAS Population (N=xxx)

					Sta				
Treatment	QMG Item ^a	Time Point ^b	Data Type ^b	Mean	Dev	n	Min	Max	Median
Amifampridine	XXXXXXXXXX	Day O (Baseline)	RAW	XXX	XXX	XXX	XXX	XXX	XXX
		Post-Baseline	RAW	XXX	XXX	XXX	XXX	XXX	XXX
			CFB	XXX	XXX	XXX	XXX	XXX	XXX
Placebo	XXXXXXXXXX	Day O (Baseline)	RAW	XXX	XXX	XXX	XXX	XXX	XXX
		Post-Baseline	RAW	XXX	XXX	XXX	XXX	XXX	XXX
			CFB	XXX	XXX	XXX	XXX	XXX	XXX

C + d

^a Table excludes limb domain items which are summarized on separate tables.

^b The post-treatment result will be the result obtained on Day 4, unless the subject discontinued treatment early, in which case the post-treatment result may be obtained at an earlier time point.

^b RAW = observed data entered in the database; CFB = change from baseline.

Table Creation Date: (DD-MMM-YYYY)

Source Program: xxxxxxx.sas

Source Listing: Data Listing 14

Table 11. QMG Item Scores Summary Statistics by Time Point and Dose Group Catalyst Pharmaceuticals, Inc. - LMS-003 FAS Population (N=xxx)

QMG Parameter = xxxxxxxxxxxxx

Treatment	Dose Group	Time Point ^a	Data Type ^b	Mean	Std Dev	n	Min	Max	Median
Amifampridine	Dobe Group	TIME FOILIE	Data Type	mean	Dev	11	11211	110221	nearan
	Low Dose (< 60mg/day)	Day 0 (Baseline)	RAW	XXX	XXX	XXX	XXX	XXX	XXX
	() , ,	Post-Baseline	RAW	XXX	XXX	XXX	XXX	XXX	XXX
			CFB	XXX	XXX	XXX	XXX	XXX	XXX
	High Dose (> 60mg/day)	Day 0 (Baseline)	RAW	XXX	XXX	XXX	XXX	XXX	XXX
		Post-Baseline	RAW	XXX	XXX	XXX	XXX	XXX	XXX
			CFB	XXX	XXX	XXX	XXX	XXX	XXX
	All Doses	Day 0 (Baseline)	RAW	XXX	XXX	XXX	XXX	XXX	XXX
		Post-Baseline	RAW	XXX	XXX	XXX	XXX	XXX	XXX
			CFB	XXX	XXX	XXX	XXX	XXX	XXX
Placebo									
	Low Dose (< 60mg/day)	Day O (Baseline)	RAW	XXX	XXX	XXX	XXX	XXX	XXX
		Post-Baseline	RAW	XXX	XXX	XXX	XXX	XXX	XXX
			CFB	XXX	XXX	XXX	XXX	XXX	XXX
	High Dose (> 60mg/day)	Day O (Baseline)	RAW	XXX	XXX	XXX	XXX	XXX	XXX
		Post-Baseline	RAW	XXX	XXX	XXX	XXX	XXX	XXX
			CFB	XXX	XXX	XXX	XXX	XXX	XXX
	All Doses	Day O (Baseline)	RAW	XXX	XXX	XXX	XXX	XXX	XXX
		Post-Baseline	RAW	XXX	XXX	XXX	XXX	XXX	XXX
			CFB	XXX	XXX	XXX	XXX	XXX	XXX

Table repeats per QMG Parameter

^a The post-treatment result will be the result obtained on Day 4, unless the subject discontinued treatment early, in which case the post-treatment result may be obtained at an earlier time point.

^b RAW = observed data entered in the database; CFB = change from baseline.

Table Creation Date: (DD-MMM-YYYY)

Source Program: xxxxxx.sas

Source Listing: Data Listing 14

Table 13. QMG Total Score CFB Analysis Catalyst Pharmaceuticals, Inc. - LMS-003 FAS Population (N=xxx)

Statistic ^a	Amifampridine	Placebo
n	XXX	XXX
Least Squares (LS) Mean of Change from Baseline (CFB)	XXX	XXX
Between-Treatment Difference in LS Means	XXX	
95% CI for Between-Treatment Difference in LS Means	(XXX, XXX)	
P-value for Between-Treatment Difference in LS Means	XXX	

^a CFB for QMG total score was modeled as the response, with fixed effects terms for treatment and QMG at Baseline. Table Creation Date: (DD-MMM-YYYY) xxxxxx.sas Source Listing: Data Listing 14

Table 15. QMG Item Scores CFB Analysis Catalyst Pharmaceuticals, Inc. - LMS-003 FAS Population (N=xxx)

QMG Item	Statistic ^a	Amifampridine	Placebo
*****	n	XXX	XXX
	Least Squares (LS) Mean of Change from Baseline (CFB)	XXX	XXX
	Between-Treatment Difference in LS Means	XXX	
	95% CI for Between-Treatment Difference in LS Means	(xxx, xxx)	
	P-value for Between-Treatment Difference in LS Means	XXX	

^a CFB for QMG item score was modeled as the response, with fixed effects terms for treatment and QMG at Baseline. A separate model was run for each QMG item. Table Creation Date: (DD-MMM-YYYY) Source Program: xxxxxxx.sas Source Listing: Data Listing 14

Table 17. SGI Score Summary Statistics by Time Point Catalyst Pharmaceuticals, Inc. - LMS-003 FAS Population (N=xxx)

Treatment	Time Point ^a	Data Type ^b	Mean	Std Dev	n	Min	Max	Median
Amifampridine	Day 0 (Baseline) Post-Baseline	RAW RAW CFB	XXX XXX XXX	XXX XXX XXX	XXX XXX XXX	XXX XXX XXX	XXX XXX XXX	XXX XXX XXX
Placebo	Day O (Baseline) Post-Baseline	RAW RAW CFB	XXX XXX XXX	XXX XXX XXX	XXX XXX XXX	XXX XXX XXX	XXX XXX XXX	XXX XXX XXX

^a The post-treatment result will be the result obtained on Day 4, unless the subject discontinued treatment early, in which case the post-treatment result may be obtained at an earlier time point. ^b RAW = observed data entered in the database; CFB = change from baseline. Table Creation Date: (DD-MMM-YYYY)

Source Program: xxxxxx.sas

Source Listing: Data Listing 13

Table 19. SGI Score Summary Statistics by Time Point and Dose Group Catalyst Pharmaceuticals, Inc. - LMS-003 FAS Population (N=xxx)

					Std				
Treatment	Dose Group	Time Point ^a	Data Type ^b	Mean	Dev	n	Min	Max	Median
Amifampridine									
	Low Dose (< 60mg/day)	Day 0 (Baseline)	RAW	XXX	XXX	XXX	XXX	XXX	XXX
		Post-Baseline	RAW	XXX	XXX	XXX	XXX	XXX	XXX
			CFB	XXX	XXX	XXX	XXX	XXX	XXX
	High Dose (> 60mg/day)	Day 0 (Baseline)	RAW	XXX	XXX	XXX	XXX	XXX	XXX
		Post-Baseline	RAW	XXX	XXX	XXX	XXX	XXX	XXX
			CFB	XXX	XXX	XXX	XXX	XXX	XXX
	All Doses	Day 0 (Baseline)	RAW	XXX	XXX	XXX	XXX	XXX	XXX
		Post-Baseline	RAW	XXX	XXX	XXX	XXX	XXX	XXX
			CFB	XXX	XXX	XXX	XXX	XXX	XXX
Placebo									
	Low Dose (< 60mg/day)	Day O (Baseline)	RAW	XXX	XXX	XXX	XXX	XXX	XXX
		Post-Baseline	RAW	XXX	XXX	XXX	XXX	XXX	XXX
			CFB	XXX	XXX	XXX	XXX	XXX	XXX
	High Dose (> 60mg/day)	Day O (Baseline)	RAW	XXX	XXX	XXX	XXX	XXX	XXX
		Post-Baseline	RAW	XXX	XXX	XXX	XXX	XXX	XXX
			CFB	XXX	XXX	XXX	XXX	XXX	XXX
	All Doses	Day O (Baseline)	RAW	XXX	XXX	XXX	XXX	XXX	XXX
		Post-Baseline	RAW	XXX	XXX	XXX	XXX	XXX	XXX
			CFB	XXX	XXX	XXX	XXX	XXX	XXX

^a The post-treatment result will be the result obtained on Day 4, unless the subject discontinued treatment early, in which case the post-treatment result may be obtained at an earlier time point.

 $^{\rm b}$ RAW = observed data entered in the database; CFB = change from baseline.

Table Creation Date: (DD-MMM-YYYY)

Source Program: xxxxxx.sas Source Listing: Data Listing 13

Table 21. SGI Score CFB Analysis Catalyst Pharmaceuticals, Inc. - LMS-003 FAS Population (N=xxx)

Statistic ^a	Amifampridine	Placebo
n	XXX	XXX
Least Squares (LS) Mean of Change from Baseline (CFB)	XXX	XXX
Between-Treatment Difference in LS Means	XXX	
95% CI for Between-Treatment Difference in LS Means	(xxx, xxx)	
P-value for Between-Treatment Difference in LS Means	XXX	

^a CFB for SGI score was modeled as the response, with fixed effects terms for treatment and QMG at Baseline. Table Creation Date: (DD-MMM-YYYY) Source Program: xxxxxx.sas Source Listing: Data Listing 13

Table 23. QMG Total Score and SGI Score Sensitivity Analysis Catalyst Pharmaceuticals, Inc. - LMS-003 FAS Population (N=xxx)

Statistic ^a	QMG Total Score	SGI Score
P-value for Between-Treatment Difference in LS Means	XXX	XXX

^a P-value based on conducting a randomization test by running the fixed effects linear model analysis on permuted treatment assignments. For each of the xxxx permutations, CFB was modeled as the response for each endpoint, with fixed effects terms for treatment and score at Baseline. Table Creation Date: (DD-MMM-YYY) Source Program: xxxxxxx.sas Source Listing: Data Listing 13, Data Listing 14

Table format will be repeated for the PP Population.

STATKING Clinical Services Version 1.0

Page 35 of 71

Page	x	of	v
ruge		 	y

Table 25.	CGI-I Scores Summary Statistics
Catalyst	Pharmaceuticals, Inc LMS-003
	FAS Population (N=xxx)

			Std					
Treatment	Time Point	Mean	Dev	n	Min	Max	Median	P-value ^a
Amifampridine	Day 4	XXX	XXX	XXX	XXX	XXX	XXX	XXX
Placebo	Day 4	XXX	XXX	XXX	XXX	XXX	xxx	

